6 INTERIM ANALYSES

No interim analysis will be conducted.

7 CHANGES IN THE PLANNED ANALYSES

A summary of all major additions, changes and deletions in the planned analyses described in the protocol will be provided in this section.

█
█
█

- Definition of PK Analysis Set was changed to set for PK Analysis Set for Lenvatinib and PK Analysis Set for Nivolumab separately.

8 DEFINITIONS AND CONVENTIONS FOR DATA HANDLING

The data will be handled as follows. The sponsor will determine how to handle all data prior to data base lock.

8.1 General Data Handling

Definition of Baseline data

Baseline is defined as the last non-missing value observed prior to the first dose of study treatment for a given parameter.

Definition of Change from Baseline, Percent Change from Baseline

Change from baseline is defined as post-baseline value minus baseline value.

Percent change from baseline is defined as follows:

$$\% \text{ Change from baseline} = (\text{Change from baseline} / \text{Baseline}) * 100\%$$

For any Baseline value of 0, the subject's corresponding percent change from baseline will not be included in the summary statistics table.

8.2 Efficacy Data Handling

Handling of missing data for tumor assessment result

For the analysis of ORR, DCR and CBR, subjects with missing response status (subjects whose baseline is missing and/or no adequate post-baseline tumor assessments result) will be coded as non-responders on Efficacy Analysis Set.

Data of tumor assessment result after documented PD or discontinuation from treatment

For the analysis of tumor assessment relevant efficacy endpoints, tumor assessment result after PD or final observation visit (for non-PD patients) are excluded from the analyses, but included in subject data listing.

Visit Windows

The purpose of visit windows is to provide a single record per subject per visit for the calculation of descriptive statistics for tumor marker per scheduled visit, and change from baseline per visit.

The observation closest to the target date will be used in by visit summaries. If two or more observations have the same distance to the target visit day, the one that has the highest value will be used for summary tables. If the multiple data in the same distance to the target date are same, the data measured at an earlier date will be used for summary tables.

The visit window is applied for tumor marker assessment summary.

Analysis visit	Target Day	Analysis Window	
		Start Day	End Day
Cycle 3 Day 1	Cycle 3 Day 1	Cycle 3 Day 1 - 7	Cycle 3 Day 1 + 7
Cycle 5 Day 1	Cycle 5 Day 1	Cycle 5 Day 1 - 7	Cycle 5 Day 1 + 7
Cycle n Day 1 (n ≥ 7 and odd numbers)	Cycle n Day 1	Cycle n Day 1 - 7	Cycle n Day 1 + 7

8.3 Safety Data Handling

Treatment-emergent adverse event

A treatment-emergent adverse event (TEAE) is defined as an AE that emerges during the time from the first dose of study drug to 30 days following the last dose of study drug, having been absent at pretreatment (Baseline) or

- Reemerged during treatment, having been present at pretreatment but stopped before treatment, or
- Worsened in severity during treatment relative to the pretreatment state, when the AE was continuous.

Adverse Events

Adverse Events with incomplete start dates will be considered treatment emergent if:

- a. Day and month are missing and the year is equal to or after the year of the first dose date;
- b. Day is missing, and the year is after the year of the first dose;
- c. Day is missing and the year is equal to the year of the first dose date and the month is equal to or after the month of the first dose date;
- d. Year is missing;
- e. Complete date is missing.

Concomitant Medications

Medications with incomplete end dates will be considered concomitant if:

- a. Day and month are missing and the year is equal to or after the year of the first dose date;

- b. Day is missing, and the year is after the year of the first dose;
- c. Day is missing and the year is equal to the year of the first dose date and the month is equal to or after the month of the first dose date; or
- d. Year is missing;
- e. Complete date is missing.

OR; complete end dates is between the date of first study dose and date of last study dose even if the start date of medications is incomplete.

TEMAV (Treatment-Emergent Markedly Abnormal Value)

Treatment-emergent markedly abnormal laboratory value (TEMAV) is defined as a postbaseline laboratory value with grade 3 or higher, and with a grade increase from baseline. (ie., Increasing grade 0 to 3 or higher, grade 1 to 3 or higher, grade 2 to 3 or higher, grade 3 to 4 or 5, grade 4 to 5.)

Handling of below lower quantification values in laboratory results

In the cases where laboratory result contains below lower quantification (BLQ) value, it will be replaced to the lower limit value of quantification (LLOQ) for summary tables.

The priority of use for blood pressure

For systolic and diastolic blood pressures, additional confirmatory assessment will be done more than 60 minutes after initial assessment, if necessary. In the case where there are both the initial and confirmatory assessment results in a day, confirmatory one will be used.

Calculation of creatinine clearance

To calculate a creatinine clearance (mL/min), the Cockcroft & Cault formula will be used.

Males: $((140 - \text{age (years)}) \times \text{weight (kg)}) / (\text{Creatinine (serum:mg/dL}) \times 72)$

Females: $((140 - \text{age (years)}) \times \text{weight (kg)} \times 0.85) / (\text{Creatinine (serum:mg/dL}) \times 72)$

Visit Windows

The purpose of visit windows is to provide a single record per subject per visit for the calculation of descriptive statistics for safety parameters (e.g., laboratory values and vital signs, etc.) per scheduled visit, and change from baseline per visit. Other safety analyses (e.g., worst grade laboratory results) will include all observations.

The observation closest to the target date will be used in by visit summaries. If two or more observations have the same distance to the target visit day, the one that has the highest CTCAE grade or is furthest away from the normal range will be used for summary tables. If

the multiple data in the same distance to the target date are in the same range from normal value, the data measured at an earlier date will be used for summary tables.

The visit window is applied for safety assessment item which is scheduled at each visit.

Analysis visit	Target Day	Visit Window	
		Start Day of Visit Window	End Day of Visit Window
Cycle 1 Day 8	Cycle 1 Day 1 + 7	Cycle 1 Day 1 + 5	Cycle 1 Day 1 + 9
Cycle 1 Day 15	Cycle 1 Day 1 + 14	Cycle 1 Day 1 + 12	Cycle 1 Day 1 + 16
Cycle 1 Day 22	Cycle 1 Day 1 + 21	Cycle 1 Day 1 + 19	Cycle 1 Day 1 + 23
Cycle 2 Day 1	Cycle 1 Day 1 + 28	Cycle 1 Day 1 + 28	Cycle 1 Day 1 + 31
Cycle 2 Day 8	Cycle 1 Day 1 + 35	Cycle 1 Day 1 + 32	Cycle 1 Day 1 + 38
Cycle 2 Day 15	Cycle 1 Day 1 + 42	Cycle 1 Day 1 + 39	Cycle 1 Day 1 + 45
Cycle 2 Day 22	Cycle 1 Day 1 + 49	Cycle 1 Day 1 + 46	Cycle 1 Day 1 + 52
Cycle n Day 1 ($n \geq 3$)	Cycle 1 Day 1 + 28 x (n-1)	Cycle 1 Day 1 + 28 x (n-1) - 3	Cycle 1 Day 1 + 28 x (n-1) + 3
Cycle n Day 8 ($n \geq 3$)	Cycle 1 Day 1 + 28 x (n-1) + 7	Cycle 1 Day 1 + 28 x (n-1) + 4	Cycle 1 Day 1 + 28 x (n-1) + 10
Cycle n Day 15 ($n \geq 3$)	Cycle 1 Day 1 + 28 x (n-1) + 14	Cycle 1 Day 1 + 28 x (n-1) + 11	Cycle 1 Day 1 + 28 x (n-1) + 17
Cycle n Day 22 ($n \geq 3$)	Cycle 1 Day 1 + 28 x (n-1) + 21	Cycle 1 Day 1 + 28 x (n-1) + 18	Cycle 1 Day 1 + 28 x (n-1) + 24
End of Treatment	30 days after last dose	Date of last dose	Date of last dose + 37

C1D1 is the day of first dosing.

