9.4.1.4 Management of Hypertension

Guidelines for assessment and management of hypertension are summarized as follows. CTCAE v4.03 grading for hypertension will be based on BP measurements only (and not on the number of antihypertensive medications).

1. When blood pressure (BP) is elevated (systolic BP ≥ 140 mmHg or diastolic BP ≥ 90 mmHg), BP measurement should be repeated at least 5 min apart. In this case, BP assessment is defined as the mean value of two measurements at least 5 minutes apart.
2. When systolic BP ≥ 140 mmHg or diastolic BP ≥ 90 mmHg is observed in the 1st BP assessment, the 2nd BP assessment should be repeated at least 30 min apart. The 2nd BP assessment is defined as the mean value of two measurements at least 5 minutes apart. For previously normotensive subjects, monotherapy with one of the classes of antihypertensives should be started when systolic BP ≥ 140 mmHg or diastolic BP ≥ 90 mmHg is firstly observed on the 2nd BP assessment. For those subjects already on antihypertensive medication, the dose of the current agent may be increased, if appropriate, or one or more agents of a different class of antihypertensives should be added.
3. If systolic BP ≥ 160 mmHg or diastolic BP ≥ 100 mmHg continues despite optimal management of hypertension, lenvatinib should be interrupted and resumed according to Table 3 at a dose of one-dose level reduction only when systolic BP ≤ 150 mmHg and diastolic BP ≤ 95 mmHg and the subject has been on a stable dose of antihypertensive medication for at least 48 hours.
4. If systolic BP ≥ 160 mmHg or diastolic BP ≥ 100 mmHg recurs despite the optimal management of hypertension, one-dose level reduction should be attempted.
5. Discontinue lenvatinib administration when Grade 4 hypertension (life-threatening) is present.

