9.5.1.5.9.2	Hepatitis B surface (HBs) antigen, HBs antibody, hepatitis B virus core (HBc) antibody, hepatitis C virus (HCV) antibody, HBV-DNA, HCV-RNA, HDV antibody or HDV RNA (hepatitis B only), and HIV antibody tests will be performed at Screening.			Hepatitis B surface (HBs) antigen, HBs antibody, hepatitis B virus core (HBc) antibody, hepatitis C virus (HCV) antibody, HBV-DNA, HCV-RNA, HDV antibody or HDV RNA (hepatitis B only), and HIV antibody tests will be performed at Screening. Data within 28 days before the first dose can be used.			

Section	Original Text (Version 2.0, 09 Jan 2018)	Amended Text (Version 3.0, 07 May 2018)	Reason of Amendment(s)
9.5.1.5.4	
Vital sign measurements (ie, systolic and diastolic BP [mmHg], pulse [beats per minute], body temperature [in centigrade]), and weight (kg) and percutaneous oxygen saturation (SPO2) will be obtained at the visits designated in the Schedule of Procedures/Assessments (Table 9) by a validated method. BP and pulse will be measured sitting after the subject has been resting. All BP measurements should be performed on the same arm, preferably by the same person. One BP assessment is defined as the mean value of 3 measurements at least 5 minutes apart. For subjects with an elevated BP (systolic BP \geq140 mmHg or diastolic BP \geq90 mmHg), confirmation should be obtained by performing 2 measurements a minimum of 1-hour apart.
	
Vital sign measurements (ie, systolic and diastolic BP [mmHg], pulse [beats per minute], body temperature [in centigrade]), and weight (kg) and percutaneous oxygen saturation (SPO2) will be obtained at the visits designated in the Schedule of Procedures/Assessments (Table 9) by a validated method. BP and pulse will be measured sitting after the subject has been resting. All BP measurements should be performed on the same arm, preferably by the same person.
	To adjust the description according to the protocol revision (Ver. 2.0).

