5.6.5 Vital Signs

Summary statistics for vital signs parameters (diastolic and systolic blood pressure, pulse, and temperature), weight, and SPO₂ and changes from baseline will be presented by visit.

Box plot display will be used to show the longitudinal change of the parameters by visit.

Subject data listings will be provided.

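### Does the SAP's 60-minute description of the confirmatory blood pressure leave it unclear which same-day value is summarised?

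*SAP*

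**What the plan says.** SAP 8.3 has a short paragraph on which blood pressure takes priority. It first describes the repeat: "additional confirmatory assessment will be done more than 60 minutes after initial assessment, if necessary". It then gives the selection rule: "In the case where there are both the initial and confirmatory assessment results in a day, confirmatory one will be used".

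Protocol 9.4.1.4 describes the repeat differently. After an elevated 1st assessment (systolic at least 140 or diastolic at least 90 mmHg), "the 2nd BP assessment should be repeated at least 30 min apart". It adds: "The 2nd BP assessment is defined as the mean value of two measurements at least 5 minutes apart". Protocol 9.5.1.5.4 (vital signs) gives no interval for a repeat.

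SAP 8.3 also has a general visit-window rule for safety parameters. When several observations lie equally far from the target day, "the one that has the highest CTCAE grade or is furthest away from the normal range will be used for summary tables". SAP 8.1 takes baseline as the last non-missing value before first dose.

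The outputs concerned are in SAP 5.6.5: by-visit summary statistics, changes from baseline, and a plot of the course over time ("Box plot display will be used to show the longitudinal change of the parameters by visit").

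**The concern.** The two documents give different intervals for what looks like the same measurement. A site that follows the protocol may repeat an elevated pressure after 40 minutes. That repeat is not more than 60 minutes after the first, so a literal reader could say that it is not confirmatory and that the blood pressure rule does not apply.

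The same-day pair would then be two observations equally far from the target day, and the tie-break would pick the worse one. The two rules pull in opposite directions: the repeat tends to lower an elevated first value, whereas the tie-break keeps it. Two programmers could produce different tables from the same data. Vital signs are also among the primary safety endpoints listed in Protocol 9.7.1.1.1 and SAP 5.1.1, so the point deserves a check.

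**Working it through.** **1. The intervals side by side.** Let t be the time in minutes from the 1st assessment to the repeat.

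| Source | Condition on t |
|---|---|
| Protocol 9.4.1.4, 2nd assessment | t ≥ 30 |
| SAP 8.3, description of the confirmatory assessment | t > 60 |
| Meets the protocol, outside the SAP description | 30 ≤ t ≤ 60 |

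A repeat after 60 minutes satisfies both. Only the last band is in question, and the documents do not say how many repeats fall in it.

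**2. What each reading selects in that band.** Take assumed readings of 162/95, then 148/88 at 40 minutes. If the repeat is confirmatory, 148/88 is summarised. If the tie-break applies, 162/95 is.

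**3. Which reading is natural.** The paragraph has two sentences and only the second selects data. It sets no time limit; it asks only whether an initial and a confirmatory result exist on that day. The protocol describes one repeat after an elevated 1st assessment, and that is the evident meaning of the confirmatory one. A rule written for blood pressure also governs a same-day blood pressure pair ahead of a general rule for all safety parameters.

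The baseline definition points the same way. The last value before dosing is the repeat, so using the repeat after baseline keeps both sides of a change from baseline on one footing. The strict reading would mix two rules.

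**4. Size on the strict reading.** The documents hold no blood pressure data, so every input except the trigger and the form of the assessments is assumed: true systolic pressure normal with mean 135 mmHg (range 125 to 145), between-subject SD 12, reading SD 6, 8 or 10, and no time effect. The trigger is 140. Diastolic pressure was not modelled, and the tie-break is taken to mean the higher systolic value.

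With F the 1st and S the 2nd assessment, the shift in the visit mean if every repeat falls in the band is

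shift = E[ (max(F, S) − S) × 1{F ≥ 140} ].

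Following the protocol, F is one reading, or the mean of two if the first reading is at least 140, and S is a mean of two. With 2,000,000 simulated subjects per cell:

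| True mean (mmHg) | Reading SD 6 | SD 8 | SD 10 |
|---|---|---|---|
| 125 | 0.37 | 0.57 | 0.82 |
| 135 | 0.98 | 1.39 | 1.83 |
| 145 | 1.70 | 2.30 | 2.90 |

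If only a fraction of repeats falls in the band, the shift scales with it. At 135:

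- 25%: 0.25 × 0.98 = 0.25 to 0.25 × 1.83 = 0.46 mmHg
- 75%: 0.75 × 0.98 = 0.74 to 0.75 × 1.83 = 1.37 mmHg

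The standard error of a 20-subject mean in this model at 135 is 2.8 to 3.1 mmHg.

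A simpler model treats each assessment as one value with SD 6 to 10. It gives 1.7 to 3.4 mmHg at 135 and 0.8 to 4.7 over 125 to 145, against a standard error of 2.9 to 3.3 at 135. It ignores the averaging in Protocol 9.4.1.4 and so overstates the effect.

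**The case for a change.** The best case for a change is that a SAP exists so that the same data give the same table, and here one sentence would remove the doubt. The strict reading is possible, the SAP does not say which rule comes first, and the shift it causes is always upward, so it would not average out over subjects. At the top of the simpler model it slightly exceeds one standard error. The 60 minutes also looks like a leftover: the protocol's change tracking shows that an earlier vital-signs section said "confirmation should be obtained by performing 2 measurements a minimum of 1-hour apart", text since removed.

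The mismatch between the current texts stands, and so does the direction of the shift. The change-log origin is conjecture and carries no weight. The claim that programmers would diverge is weaker than it looks. SAP 8 has the sponsor decide data handling before database lock, SAP 9 places derivation rules in separate specifications, and SAP 10 requires validated standard programs or double programming. None of this proves that the point has been settled, but it is where such a detail is normally settled.

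Little rests on the outcome. SAP 5.3.3 plans no statistical comparison. Analyses other than the by-visit summaries use all observations, the listings are provided, and adverse events are graded by the investigator.

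**Conclusion.** This is a clerical mismatch of intervals, which analysts would resolve by using the protocol's 2nd assessment whatever its timing. On that reading the reported values do not change at all.

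On the strict reading, the effect is confined to post-baseline by-visit summaries, changes from baseline (through the post-baseline value only) and box plots. It is at most 1.0 to 1.8 mmHg at an assumed true mean of 135, or about 0.2 to 1.4 mmHg if 25% to 75% of repeats are affected. Both ranges lie below one standard error of a 20-subject mean. They rest on the assumed mean, SDs and repeat timing; over true means of 125 to 145 the upper bound runs from 0.4 to 2.9 mmHg.

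No test, DLT decision, adverse event grade or study conclusion depends on the choice. Aligning the wording would be tidy but would gain nothing of substance, so no change to the plan is called for. No view is taken on which clinical interval is right.

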9.5.1.5.3 LABORATORY MEASUREMENTS

Clinical laboratory tests to be performed, including hematology, chemistry, and urinalysis, are summarized in Table 8. The Schedule of Procedures/Assessments (Table 9) shows the visits and time points at which blood for clinical laboratory tests and urine for urinalysis will be collected in the study. Clinical laboratory tests will be performed at each site.

Table 8 Clinical Laboratory Tests

Category	Parameters
Hematology	RBC count, hemoglobin, hematocrit, platelets, and WBC count with differential (basophils, eosinophils, lymphocytes, monocytes, neutrophils)
Anticoagulant test	INR ^a
Chemistry	
Liver function tests	Alkaline phosphatase, aspartate aminotransferase, alanine aminotransferase, gamma glutamyl transpeptidase, total bilirubin, direct bilirubin
Renal function tests	Blood urea nitrogen, creatinine
Other	Glucose, albumin, total cholesterol, triglycerides, phosphorus, lactate dehydrogenase, total protein, sodium, potassium, chloride, calcium, magnesium, ammonia ^b , amylase ^c , lipase ^c , ACTH ^e , cortisol ^e
Tumor marker	AFP
Thyroid function tests	TSH, FT4
Virus tests ^b	HIV antibody, HCV antibody, HBs antigen, HBs antibody, HBc antibody, HBV DNA, HCV RNA, HDV antibody or HDV RNA ^d
Urinalysis	pH, protein, glucose, ketones, RBCs, specific gravity

AFP = α -fetoprotein, INR = International Normalized Ratio

a: INR will be assessed on C2D1 and every cycle thereafter.

b: Screening only. Data within 28 days before the first dose can be used.

c: Amylase and lipase will be measured at Screening, C2D1 and every cycle thereafter.

d: Subjects with hepatitis B only

e: If necessary, appropriate laboratory tests such as adrenal cortical function test (ACTH, cortisol) to be added.

A laboratory abnormality may meet the criteria to qualify as an AE as described in this protocol (see Section 9.5.1.5.1). In these instances, the AE corresponding to the laboratory abnormality will be recorded on the CRF. If AEs were assessed during unscheduled visits, all the data corresponding to the laboratory abnormality will also be recorded on the CRF.

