
C#D# = Cycle#/Day#, ECOG-PS = Eastern Cooperative Oncology Group performance status, INR= international normalized ratio, MUGA= multiple gated acquisition scan.
 
a: Screening assessment should be initiated after obtaining informed consent (Informed consent can be obtained within 28 days of first dose).
 
b: Height (Screening only)
 
c: Virus test (Screening only), Data within 28 days before the first dose can be used), Ammonia test (Screening only), Hematology, blood chemistry, urinalysis, blood coagulation tests, thyroid function test. If necessary, appropriate laboratory tests such as adrenal cortical function test (ACTH, cortisol) to be added.
 
d: Effort should be made to obtain during study. Exclude subjects without available archival tissues.
 
e: Only in Part 2. Exclude subjects with inaccessible tumors for biopsy of safety concern.
 
f: Data within 3 months before the first dose can be used (data before obtaining informed consent can also be used).
 
g: Data within 28 days before the first dose can be used (data before obtaining informed consent can also be used).
 
h: Regarding tests which are performed in both screening and baseline, if screening test is done 4 days before first dose, baseline tests are not required.
 
i: For Part 1, blood collection at predose, 1, 2, 4, 8, 24 hours postdose of Cycle 1 Day1 and Day 15, and predose of Day 1 of every cycle thereafter. However, blood collection is not required after Cycle 24. For Part 2, blood collection at 0.5 - 4 hours postdose of Cycle1 Day1, pre and 0.5 - 4 hours postdose of Cycle1 Day15 and predose of Cycles 2, 4, 6
 
j: CT assessments (including tumor marker assessment) will be performed every 8 weeks (Day 1 [± 7 days] in odd number cycle) from Day 1 of Cycle 1, or more frequently if disease progression is clinically indicated.
 
k: Subjects will be hospitalized until completion of Cycle 1 in Part 1. Outpatient is allowed after C1D15 when investigator or subinvestigator judges that the subject's safety is ensured.
 
l: +3 days in C2D1 (Part 1 only)
 
m: Cycle 3 or later, test items can be omitted only when investigator or subinvestigator judges that that the subject's safety is ensured.
 
n: Predose
 
o: Data within 7 days before discontinuation, if available, can be used as the discontinuation data.
 
p: Data within 28 days before off treatment, if available, can be used as the discontinuation data.
 
q: If a new anticancer agent needs to be immediately started due to deterioration in the subject's condition, the last observation visit can be conducted before 30 days after the last dose of the study drug has passed but prior to starting the new anticancer agent. If the last observation visit occurs within 7 days after study drug discontinuation, discontinuation data can be used as the last observation data.
 
r: Only in Part 2. Every 12 weeks (± 2 weeks) from last observation visit
 
s: Predose and just before completion of nivolumab administration
 
t: Predose of Cycles 2, 3, 4, 5, 9, 13 (thereafter every 4 cycles) and just before completion of nivolumab administration in Cycle 5
 
u: Predose of Cycle 5
 
v: Predose of Cycles 2, 3, 5, 9, 13 (thereafter every 4 cycles)
 
w: Part 2 only. Predose of Cycles 1 and 3. When the subject discontinues the study before sampling of Cycle 3, the sampling at discontinuation visit should be done.
	

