5.6.4 Laboratory Values

Laboratory results will be summarized using Système International (SI) units. For all quantitative parameters, the actual value and the change from baseline to each postbaseline visit will be summarized by visit using summary statistics. Qualitative parameters will be summarized by number and percentage of subjects, and changes from baseline to each postbaseline visit will be reported using shift tables. Percentages will be based on the number of subjects with both nonmissing baseline and relevant postbaseline results.

Box plot display will be used to show the longitudinal change of the parameters by visit.

Laboratory test results will be assigned a low/normal/high (LNH) classification according to whether the value is below (L), within (N), or above (H) the laboratory parameter's reference range. The result of LNH classification will be provided in a subject data listing.

Laboratory parameters will be graded by CTCAE ver. 4.03 in the [section 13](#). Changes from CTCAE grade at baseline to each postbaseline visit and worst postbaseline will be reported using shift tables. CTCAE will also be used to identify subjects with Treatment-emergent markedly abnormal laboratory value (TEMAV). The number (percentage) of subjects with TEMA (markedly abnormal high/low) will be summarized for each visit and overall study period. The TEMA will be defined in the [section 8.3](#).

Subject data listings will be provided.

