5.6.7 Other Safety Analyses

LVEF

Descriptive statistics for LVEF and LVEF changes from baseline assessed by MUGA scans or echocardiograms will be summarized by visit.

Subject data listings will be provided.

ECOG PS

The number (percentage) of subjects for each category of ECOG PS will be summarized by visit. The highest postbaseline scale of ECOG PS for each subject will also be summarized.

Subject data listings will be provided.

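### The SAP's Cycle 2 Day 1 visit window uses the Part 1-only allowance for both parts, so compliant Part 2 visits on C1D1+25 to +27 fall in no scheduled-visit window

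*SAP*

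**What the plan says.** Protocol 9.5.2.1, Table 9, gives Day 1 of Cycle 2 and every later cycle an allowance of ±3 days and attaches footnote l. That footnote makes the allowance at C2D1 late-only, with a plus sign before "3 days in C2D1 (Part 1 only". Part 2 therefore keeps the full ±3 days.

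The Visit Windows table in SAP 8.3 has a single C2D1 row with no split by part. It starts at C1D1+28 and ends at "Cycle 1 Day 1 + 31". The row before it, Cycle 1 Day 22, ends at "Cycle 1 Day 1 + 23", and the row after it, Cycle 2 Day 8, starts at C1D1+32. From Cycle 3 onward the SAP does use ±3 days for Day 1.

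The windows feed the by-visit summaries only. For the rest, the same section says "Other safety analyses (e.g., worst grade laboratory results) will include all observations".

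**The concern.** The C2D1 row reproduces the Part 1 rule exactly and applies it to both parts. A Part 2 subject who attends one to three days early has complied with the protocol, but the record belongs to no scheduled row of the SAP table. If the table is programmed as printed, the record is left out of the Part 2 C2D1 column, and scheduling alone decides who is missing.

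The tables exposed are the by-visit descriptive, change-from-baseline and shift tables, and the count of markedly abnormal laboratory values, which SAP 5.6.4 says "will be summarized for each visit and overall study period". Laboratory tests, vital signs, ECG and ECOG-PS are named primary safety endpoints (SAP 5.1.1).

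C2D1 is also not just one visit among many. Table 9 schedules no ECOG-PS between baseline and C2D1, so this column holds the first post-baseline value, and SAP 5.6.7 says "The number (percentage) of subjects for each category of ECOG PS will be summarized by visit". Protocol Table 8 places the first on-treatment coagulation and pancreatic tests there too: "INR will be assessed on C2D1 and every cycle thereafter" and "Amylase and lipase will be measured at Screening, C2D1 and every cycle thereafter".

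**Working it through.** All days are offsets from C1D1, on the nominal 28-day calendar that the SAP windows use.

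**Inputs**
- Cycle length 28 days (SAP 3.2.3.2).
- Allowance for Day 1 of Cycle 2 or later: ±3 days, but +3 only at C2D1 in Part 1 (Protocol Table 9 and footnote l).
- SAP 8.3 windows: Cycle 1 Day 22, +19 to +23; C2D1, +28 to +31; Cycle 2 Day 8, +32 to +38.

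**Reproducing the SAP row.** The target for Day 1 of cycle n is 28 × (n − 1). For n = 2 this is +28. The Part 1 rule gives 28 to 28 + 3, that is +28 to +31 (4 days), which is exactly the SAP row.

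**Part 2.** 28 − 3 to 28 + 3 gives +25 to +31 (7 days).

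| Offset from C1D1 | Permitted for C2D1 in Part 2? | SAP scheduled-visit window |
|---|---|---|
| +19 to +23 | No | Cycle 1 Day 22 |
| +24 | No | none |
| +25, +26, +27 | **Yes** | **none** |
| +28 to +31 | Yes | C2D1 |
| +32 to +38 | No | Cycle 2 Day 8 |

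Uncovered share of permitted days: 3/7.

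**Is the row an exception within the SAP?** The SAP's own Day 1 formula for n ≥ 3 is 28 × (n − 1) ± 3. With n = 2 it gives +25 to +31, not the printed row. The other Cycle 2 rows do match the general formulas at n = 2: Day 8 is 28 + 4 to 28 + 10 = +32 to +38, Day 15 is 28 + 11 to 28 + 17 = +39 to +45, and Day 22 is 28 + 18 to 28 + 24 = +46 to +52. A day-by-day comparison of Table 9 with the SAP windows from Cycle 1 Day 8 to Cycle 5 Day 22 finds one mismatch, C2D1 in Part 2, and none in Part 1.

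**End of Treatment row.** This runs from the last dose to 37 days after it. It could hold a record from +25 to +27 only if the last dose was on or before that day, so it does not help a subject who continues treatment.

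**Size in subjects.** The documents give no attendance pattern, so the range is 0 to 20 of the 20 Part 2 subjects. As an illustration only, assume that all 20 reach C2D1 and that early attenders have no other record on +28 to +31:
- 5% early: 20 × 0.05 = 1 missing
- 10% early: 20 × 0.10 = 2 missing
- 20% early: 20 × 0.20 = 4 missing

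SAP 5 also reports the 8 mg and 12 mg groups separately. With 20 subjects and at least 5 in each group, a group has between 5 and 20 − 5 = 15 subjects. Each missing record is then 1/5 = 20% to 1/15 = 6.7% of a dose-group column.

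**The case against.** The strongest reply is that the SAP nowhere says an out-of-window record is discarded. SAP 8.3 tells the analyst to use the record nearest the target day, SAP 8 leaves data handling to the sponsor before lock, and SAP 9 places derivation rules in separate documents that are not in the file. Those documents might assign the records. This part stands, so the loss is what the printed table produces, not a proven outcome. It does not cure the table. The nearest-record rule chooses among candidates for a visit whose start and end days are stated; read as assigning any record to its nearest visit, it would leave those limits with nothing to do. The other two are general deferrals that say nothing about C2D1.

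A second reply concerns scope. The SAP applies the windows to items scheduled at each visit, and ECOG-PS, INR, amylase and lipase are not collected at every visit. The natural reading is that each item is windowed at its own scheduled visits, and a by-visit count of abnormal values needs a visit assignment in any case. The INR timing is not uniform in the protocol: footnote c of Table 9 includes coagulation tests in a laboratory row that is also marked in Cycle 1. Table 8 is the more specific statement, but the claim about the first on-treatment INR rests on it alone.

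Third, 3 of 7 days is not a probability. C2D1 is a nivolumab dosing day, so early attendance may be uncommon, and the 5% to 20% rates have no source. That is right, and no expected count is claimed.

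Finally, the consequence is small. That also stands, and it sets the priority.

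**Conclusion.** The point holds. SAP 8.3 contradicts Protocol Table 9 for Part 2 at C2D1: 3 of the 7 permitted days are in no scheduled-visit window, against none at every other row checked on the nominal calendar. The readable part of SAP 7 records no decision to narrow the window for Part 2.

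The impact is low. One by-visit column in one part is exposed. AE tables, worst-postbaseline grade shifts, markedly abnormal values over the whole study period, the at-least-once QTcF criteria, highest postbaseline ECOG-PS and all listings keep the data. The SAP plans no statistical comparison and no interim analysis, the DLT evaluation is confined to Part 1, and the row is correct for Part 1. The number of subjects lost is unknown and could be zero. The conclusion rests on reading the window limits as limits and on no unseen programming rule overriding them. It should be corrected because protocol-compliant primary safety data should not depend on such a rule.

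**What to change.** In the Visit Windows table of SAP 8.3, replace the single C2D1 row with two:
- Part 1: C1D1+28 to C1D1+31 (unchanged)
- Part 2: C1D1+25 to C1D1+31

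The Part 2 row overlaps neither Cycle 1 Day 22 (ends +23) nor Cycle 2 Day 8 (starts +32). Repeating the day-by-day comparison with this row leaves no compliant Part 2 day uncovered from Cycle 1 Day 8 to Cycle 5 Day 22; the gaps that remain before C2D1 (+10, +11, +17, +18, +24) lie outside any protocol allowance.

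The cost is one table row in the SAP and one condition on study part in the programs. No protocol text, visit schedule or clinical rule changes.
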